#### 8.11. Assessment of compliance with treatment

As only two doses of the drug are being taken 24 hours apart, adherence is expected to be high. Sites will record when the first dose is taken on the eCRF. Participants will be asked to confirm whether they have taken their second dose via their 3rd SMS survey (T3).

Term	Definition					
Adverse Event (AE)	Any untoward medical occurrence in a participant to whom a medicinal product has been administered, including occurrences which are not necessarily caused by or related to that product.					
Adverse Reaction (AR)	An untoward and unintended response in a participant to an investigational medicinal product which is related to any dose administered to that participant.					
	The phrase "response to an investigational medicinal product" means that a causal relationship between a trial medication and an AE is at least a reasonable possibility, i.e. the relationship cannot be ruled out.					
	All cases judged by either the reporting medically qualified professional or the Sponsor as having a reasonable suspected causal relationship to the trial medication qualify as adverse reactions. It is important to note that this is entirely separate to the known side effects listed in the SmPC. It is specifically a temporal relationship between taking the drug, the half-life, and the time of the event or any valid alternative aetiology that would explain the event.					
Serious Adverse	A serious adverse event is any untoward medical occurrence that:					
Event (SAE)	
 
Results in death.
 
Is life-threatening; an event in which the participant was at risk of death at the time of the event. This does not refer to an event which hypothetically might have caused death if it were more severe.
 
Requires inpatient hospitalisation or prolongation of existing hospitalisation.
 
Results in persistent or significant disability/incapacity.
 
Consists of a congenital anomaly or birth defect.
 
					
	Other 'important medical events' may also be considered serious if they jeopardise the participant or require an intervention to prevent one of the above consequences.					
	In this trial the following conditions will always be reported as serious adverse events:					

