	
 
Gastrointestinal bleeds
 
Psychosis
 
Severe hyperglycaemia (defined for this trial as ketoacidosis, hyperglycaemic hyperosmolar state or hyperglycaemia requiring new use of insulin)
 
					
Serious Adverse Reaction (SAR)	An adverse event that is both serious and, in the opinion of the reporting Investigator, believed with reasonable probability to be due to the trial treatment, based on the information provided.					

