#### 9. PHARMACOVIGILANCE
Suspected Unexpected Serious	A serious adverse reaction, the nature and severity of which is not consistent with the information about the medicinal product in
Adverse Reaction (SUSAR)	question set out in the reference safety information.

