# 9.4. Recording and reporting of SAEs, SARs AND SUSARs

The recording and reporting requirements are summarised in the safety reporting flowchart in appendix 1.

All serious adverse events (whether related or not) should be reported to ExeCTU within 24 hours of the event being assessed as serious by completing the 'SAE' eCRF in REDCap. All SAE eCRFs must

be reviewed and signed off by a Principal Investigator (PI) or delegated medic within REDCap. In the event of a death the 'Notification of Death' eCRF should also be completed in REDCap.

Information not available at the time of the initial report (e.g. test results) must be added to the SAE eCRF by the site team as soon as it becomes available.

ExeCTU will receive an automated email notification to alert them to a new SAE eCRF or when a change is made to an SAE eCRF. For events occurring up to Day 14 (post-randomisation) ExeCTU will onward report all SAEs to the Sponsor within 24 hours of becoming aware of the event. For events occurring from Day 15 to Day 90, ExeCTU will onward report SUSARs to the Sponsor within 24 hours of becoming aware but all other SAEs reported from Day 15 onward will be reviewed by the sponsor in bulk (e.g. as listed in TMG reports).

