# 9.4.1. Reviewing serious adverse events

The CI or designated representative will review all reported SAEs to assess relatedness, and where related, assess expectedness to the IMP against the RSI. The CI will not downgrade a PI's assessment of relatedness, however they may upgrade a PI's assessment of relatedness (i.e. from unrelated to related).

Sites should respond as soon as possible to requests for further information by the CI or designated representative required for the final assessment of the SAE.

In the event of a SUSAR, the Sponsor or ExeCTU will take responsibility for unblinding prior to submission of the SUSAR to the MHRA and the REC. Investigators will only receive information on the results of the unblinding if it is judged necessary for the safety of the participant.

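### Section 9.1 of the Protocol sets a stricter causality test for a serious adverse reaction than for an adverse reaction, so a possibly related serious event may be under-classified and miss expedited reporting

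*Protocol*

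**What the plan says.** All references are to the Protocol.

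- **Adverse reaction (AR), Section 9.1.** Causality suffices if it "is at least a reasonable possibility, i.e. the relationship cannot be ruled out". The row also says who decides: "All cases judged by either the reporting medically qualified professional or the Sponsor as having a reasonable suspected causal relationship" to the trial medication.
- **Serious adverse reaction (SAR), same table.** The event must be serious and, "in the opinion of the reporting Investigator, believed with reasonable probability to be due to the trial treatment".
- **SUSAR, same table.** "A serious adverse reaction, the nature and severity of which is not consistent with the information about the medicinal product in" question, as set out in the reference safety information.
- **Section 9.3.** Seriousness, severity and relatedness are assessed using the Section 9.1 definitions, as if the participant had received the active drug.
- **Section 9.4.** "All serious adverse events (whether related or not) should be reported to ExeCTU within 24 hours of the event being assessed as serious". "For events occurring up to Day 14 (post-randomisation) ExeCTU will onward report all SAEs to the Sponsor within 24 hours of becoming aware". From Day 15 to Day 90 only SUSARs go on within 24 hours; the Sponsor reviews other SAEs in bulk. Appendix 1 likewise has SAEs and SARs go in batches after Day 14.
- **Section 9.4.1.** The CI or a representative reviews every SAE for relatedness and, where related, for expectedness. The CI may not downgrade the site's view, but "they may upgrade a PI's assessment of relatedness (i.e. from unrelated to related").
- **Section 9.4.4.** The 7- and 15-calendar-day reports to the MHRA and REC start from a SUSAR.
- **Section 9.5.** The CI reviews SAE causality using medical judgement, and reviews SARs for expectedness.

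**The concern.** A SAR should be an adverse reaction that is also serious. Here the two rows differ on the threshold (possibility against probability) and on who may apply it (reporter or Sponsor against the reporting Investigator alone). The stricter test falls on the more serious events, and the SUSAR definition inherits it.

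What is at stake is expedited safety reporting. Someone applying the SAR row as written could leave a possibly related serious event outside the SAR class, and so outside the SUSAR class, and the regulator, the REC and the other sites might not hear of it on time. The Protocol's own risk section makes this more than a matter of style. It classes the trial as Type B, notes that there is less randomised evidence on harms of short-term steroids than on chronic use, and mentions possible under-reporting of hyperglycaemia in earlier trials.

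**Working it through.** No arithmetic decides this; it turns on how the definitions fit together. Take a serious event that is not consistent with the reference safety information, and read each row literally.

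| Causality view | AR row met? | SAR row met? | Can it be a SUSAR? |
|---|---|---|---|
| A. Investigator: reasonably probable | Yes | Yes | Yes |
| B. Investigator: cannot be ruled out, but not probable | Yes | No | No |
| C. Investigator: unrelated; Sponsor: reasonable suspicion | Yes | No | No |
| D. Investigator: unrelated; CI upgrades to related | Not addressed (the row names the reporter and the Sponsor, not the CI) | No | No, although 9.4.1 calls for expectedness review |
| E. All: unrelated | No | No | No |

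The rows agree for A and E. They contradict each other for B and C. For D the table is out of step with Section 9.4.1.

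Next, follow cases B to D through the reporting steps.

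1. **Site assessment.** Section 9.3 points to Section 9.1 for relatedness. Section 9.1 holds both tests and does not say which prevails for a serious event.
2. **Trials unit.** All SAEs arrive within 24 hours whatever the causality. B, C and D are all caught here.
3. **Sponsor, to Day 14.** All SAEs arrive within 24 hours. B, C and D are all caught, and the Sponsor can form its own view.
4. **Sponsor, Day 15 to Day 90.** This is 90 − 14 = 76 of the 90 days after randomisation. Only SUSARs arrive within 24 hours. An event held not to be a SAR is not a SUSAR, so it waits for the bulk review. In case C, the Sponsor's separate view, on which the AR row relies, may then come late.
5. **CI review.** It covers every SAE at all times and can upgrade. Section 9.4.1 gives no causality threshold of its own, so the CI has the same two rows to draw on. Its trigger for expectedness review is that the event is related, whereas Section 9.5 refers to SARs.
6. **Expedited report.** Section 9.4.4 starts from a SUSAR, and so from the SAR row.

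The documents give no expected number of serious or related events, so the number that might fall into B, C or D cannot be calculated.

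**The case against.** The strongest reply is that the site's SAR label does not decide whether expectedness is reviewed. Under Section 9.4.1 the CI looks at every SAE and goes on to expectedness wherever the event is related. Only the AR row explains what related means, and it uses the low threshold; the SAR row can be read as naming a category without redefining the term. All SAEs reach the trials unit within 24 hours and, to Day 14, the Sponsor too. Gastrointestinal bleeds, psychosis and severe hyperglycaemia are always serious. Treatment is two doses about 24 hours apart, with an effect expected over the following 24 to 48 hours, so a drug link is most plausible well inside the first 14 days, when forwarding is complete.

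Much of this stands, and it rules out several stronger readings that a reader might infer:

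- That possibly related serious events will escape expedited reporting. Reporting of all SAEs and CI review make this a risk only.
- That sites will mark such events as unrelated. The SAE form is not in the documents, so its wording is unknown.
- That possible is the usual causality verdict, or that a definable grade of events is lost. The Protocol describes no graded scale; Section 9.4.1 speaks only of unrelated and related.
- That the effect is larger after Day 14. The safeguards are weaker then, but fewer drug-related events may arise.

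What does not stand is that the safeguards settle the matter. They move the event to another assessor without saying which causality test applies. If the SAR row is read as only a category label, its own causality clause and its restriction to the reporting Investigator have no purpose.

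**Conclusion.** The inconsistency is real and should be corrected. Section 9.1 sets two conflicting causality tests with different decision-makers, and the SUSAR definition rests on the stricter one. A serious, unexpected event that is possibly but not probably related, or that only the CI or Sponsor considers related, may be under-classified and miss the 7- or 15-day report. The existing safeguards reduce that risk without removing it, and cover is weakest from Day 15 to Day 90.

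The size cannot be stated in events. The conclusion assumes only that assessors apply the definitions as written, as Section 9.3 asks. It does not affect the primary outcome, the sample size or the efficacy analysis.

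**What to change.** Replace the SAR row with a definition that refers back to the AR row: an adverse reaction, by the Protocol's existing AR test and assessors, that also meets a seriousness criterion. State that an event the CI upgrades under Section 9.4.1 counts as related for this purpose; the AR row does not name the CI, so a cross-reference alone would leave case D open. The SUSAR row then needs no change. Use the same causality wording for relatedness on the SAE form, and align Section 9.5 with Section 9.4.1 so that expectedness review follows whenever a serious event is related.

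The cost is one table row, a sentence in Section 9.5 and a check of the form's prompt. The downside is that slightly more SAEs will be classed as related and go through expectedness review.

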#### 9. PHARMACOVIGILANCE
Suspected Unexpected Serious	A serious adverse reaction, the nature and severity of which is not consistent with the information about the medicinal product in
Adverse Reaction (SUSAR)	question set out in the reference safety information.

#### Severity classifications

Mild event	An event that is easily tolerated by the patient, causing minimal discomfort and not interfering with everyday activities.
Moderate event	
	activities.
Severe event	An event that prevents normal everyday activities.

#### 9.2. Expected adverse events associated with the study drug

The reference safety information (RSI) for this study is section 4.8 of the supplied pharmacovigilance reference copy of the dexamethasone SmPC.

#### 9.3. Recording and reporting adverse events

The safety reporting period will begin at the time of randomisation up to the 90-day follow-up timepoint. The recording and reporting requirements are summarised in the safety reporting flowchart in appendix 1.

Only serious or related adverse events (AR/SAE/SAR/SUSAR) need to be recorded in the eCRF, from the time of randomisation up to the 90-day follow-up timepoint. All adverse events should be recorded in the participant's medical notes.

All adverse events will be assessed for seriousness, severity and relatedness to the study drug as per the definitions in section 9.1 above. These assessments should be carried out by the site PI, or delegated medic and recorded in the medical notes (and eCRF where serious or related).

Important: please note that psychosis, gastrointestinal bleeds and severe hyperglycaemia should always be classified as serious in this trial. Severe hyperglycaemia is defined for this trial as ketoacidosis, hyperglycaemic hyperosmolar state or hyperglycaemia requiring new use of insulin.

As this is a blinded trial, adverse events should be evaluated on the assumption that the participant was allocated the active drug i.e. dexamethasone. The blind should only be broken where knowing the allocation is clearly necessary and will alter the appropriate medical management of the patient. If unblinding is necessary, please refer to the Emergency Unblinding section of the protocol (7.7.0) and the 'Unblinding' working instruction.

# 9.4. Recording and reporting of SAEs, SARs AND SUSARs

The recording and reporting requirements are summarised in the safety reporting flowchart in appendix 1.

All serious adverse events (whether related or not) should be reported to ExeCTU within 24 hours of the event being assessed as serious by completing the 'SAE' eCRF in REDCap. All SAE eCRFs must

be reviewed and signed off by a Principal Investigator (PI) or delegated medic within REDCap. In the event of a death the 'Notification of Death' eCRF should also be completed in REDCap.

Information not available at the time of the initial report (e.g. test results) must be added to the SAE eCRF by the site team as soon as it becomes available.

ExeCTU will receive an automated email notification to alert them to a new SAE eCRF or when a change is made to an SAE eCRF. For events occurring up to Day 14 (post-randomisation) ExeCTU will onward report all SAEs to the Sponsor within 24 hours of becoming aware of the event. For events occurring from Day 15 to Day 90, ExeCTU will onward report SUSARs to the Sponsor within 24 hours of becoming aware but all other SAEs reported from Day 15 onward will be reviewed by the sponsor in bulk (e.g. as listed in TMG reports).

# 9.4.1. Reviewing serious adverse events

The CI or designated representative will review all reported SAEs to assess relatedness, and where related, assess expectedness to the IMP against the RSI. The CI will not downgrade a PI's assessment of relatedness, however they may upgrade a PI's assessment of relatedness (i.e. from unrelated to related).

Sites should respond as soon as possible to requests for further information by the CI or designated representative required for the final assessment of the SAE.

In the event of a SUSAR, the Sponsor or ExeCTU will take responsibility for unblinding prior to submission of the SUSAR to the MHRA and the REC. Investigators will only receive information on the results of the unblinding if it is judged necessary for the safety of the participant.

# 9.4.2. Ongoing events

Some SAEs/SARs/SUSARs may be ongoing at the time of initial reporting.

It is the PI or delegated clinician's responsibility to ensure that that all participants with ongoing SAEs/SARs/SUSARs are followed up until the final outcome is reached or until the Sponsor and CI agree that no further follow-up is required.

There is no mandatory requirement regarding the frequency which follow-up reports should be submitted. All follow-up information should be entered into the eCRF as soon as possible after the PI or designated representative becomes aware of an update. As a minimum, a report should be submitted when the event resolves/ends.

Ongoing SAEs/SARs/SUSARs at the end of the trial will be followed up by the participant's GP and/or the routine clinical care team until discharge.

# 9.4.3. Notification of deaths

Irrespective of whether the death is related to the intervention or if it is unrelated, all deaths occurring during the safety reporting period must be reported to ExeCTU and the Sponsor **within 24 hours** of the PI or research team becoming aware of the event. This will be reported by completing an 'SAE' eCRF in REDCap. The 'Notification of Death' eCRF should also be completed in REDCap.

# 9.4.4. Expedited reporting of SUSARs

If a SUSAR is reported by a site, the Sponsor will coordinate onward reporting to the REC and the MHRA (within **7 calendar days** of receipt of the initial report for fatal/life-threatening events or **15 calendar days** of receipt of the initial report for non-fatal/non life-threatening events)

All other recruiting sites will be informed of the SUSAR by ExeCTU.

#### 9.5. Responsibilities

The CI is responsible for oversight of the safety of participants in the trial, including an ongoing review of the risk/benefit. They will review SAEs causality using their medical judgement and review all SARs for expectedness using the RSI in a timely manner.

The CI (or delegate) will assign Medical Dictionary for Regulatory Activities (MedDRA) coding to all reportable safety events.

# 9.6. Pregnancy reporting

In the event of a pregnancy being reported by a female participant, this must be reported using an ExeCTU 'Pregnancy' eCRF within 24 hours of learning of its occurrence. Pregnancies from randomisation until Day 14 should be reported. If the pregnancy is not known until after this time frame, it should still be reported if conception was during this period. As dexamethasone is not known to have harmful effects on male fertility/health of children conceived by males taking dexamethasone, pregnancies in partners of male participants will not be reported.

If a pregnancy is reported during the intervention period, the participant should be withdrawn from the intervention and instructed not to take any further doses of the study drug, however, they can continue to complete follow-up. If pregnancy is reported after the intervention period they should continue with follow-up as planned unless the participant requests otherwise. No additional follow-up is required for participants who become pregnant during the trial.

Pregnancy is not considered an AE unless a negative or consequential outcome is recorded for the mother or child/foetus. If the outcome meets the serious criteria, this would be considered an SAE.

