#### 6. PARTICIPANT ELIGIBILITY CRITERIA

#### 6.1. Inclusion criteria

- Aged 16 years old or over
- A current clinical diagnosis of cellulitis at any body site except the orbit (periorbital/orbital cellulitis)
- Able to provide informed consent

People of child-bearing\* potential must be willing to:

- Use an effective method of contraception\*\* (and must agree to continue 3 months after the last dose of the IMP)
- Inform the trial team if pregnancy occurs during trial participation

\* Potential participants are considered not of child-bearing potential if they are surgically sterile (i.e. they have undergone a hysterectomy, bilateral salpingectomy, or bilateral oophorectomy) or they are postmenopausal (no menses for 12 months without an alternative medical cause).

\*\* Highly effective contraception is defined as one of the following: combined (oestrogen and progestogen containing) hormonal contraception associated with inhibition of ovulation (oral, intravaginal, or transdermal); progestogen-only hormonal contraception associated with inhibition of ovulation (oral, injectable, or implantable); intrauterine device(IUD); intrauterine hormone-releasing system (IUS); bilateral tubal occlusion; vasectomised

partner; practising true sexual abstinence (when this is in line with the preferred and usual lifestyle of the individual).

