#### 6.2. Exclusion criteria

Participants may not enter trial if ANY of the following apply:

- Orbital or periorbital cellulitis, surgical site infection, or planned surgical management (e.g abscess) as managed under a different clinical pathway
- Allergy to dexamethasone
- Contraindication to dexamethasone due to concurrent medication (e.g. cobicistat)
- Has known current invasive fungal infection\*\*
- Has known current gastric or duodenal ulceration
- Already on corticosteroids
- Unable to take oral medication
- Lack of capacity
- Inability to complete follow-up procedures
- Prisoner\*

People of child-bearing potential only:

• Pregnant\*\*\*, breastfeeding, or planning to conceive in next 3 months

\*This does not exclude patients in police custody, though consideration should be given to whether they are able complete the trial follow-up procedures.

\*\* This includes only invasive infections such as pulmonary aspergillosis and does NOT include cutaneous infections such as athlete's foot, vaginal thrush, etc.

\*\*\*Must have a negative pregnancy test no more than 7 days prior to initiation of treatment.

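### Section 9.6 does not require a report of a pregnancy already present at dosing but first known after Day 14, and no procedure collects pregnancy outcomes after Day 90

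*Protocol*

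**What the plan says.** Protocol section 9.6 opens with a general duty to enter a participant's pregnancy on the Pregnancy eCRF within 24 hours of learning of it. It then sets a window: "Pregnancies from randomisation until Day 14 should be reported". For a pregnancy that comes to light after that window, the condition is that "it should still be reported if conception was during this period".

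On outcomes, the same section says: "Pregnancy is not considered an AE unless a negative or consequential outcome is recorded for the mother or child/foetus". An outcome that meets the seriousness criteria becomes an SAE, and the SAE definition in section 9 includes an event that "Consists of a congenital anomaly or birth defect". Section 9.6 then adds: "No additional follow-up is required for participants who become pregnant during the trial". Section 9.3 ends the safety reporting period at the 90-day follow-up, and section 7.11 ends the participant's trial there too.

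On eligibility, section 6.2 says of people of child-bearing potential: "Must have a negative pregnancy test no more than 7 days prior to initiation of treatment". Section 7.3 repeats this. Section 6.1 asks participants to use contraception ("must agree to continue 3 months after the last dose of the IMP") and to do the following: "Inform the trial team if pregnancy occurs during trial participation".

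**The concern.** Two gaps follow from these rules.

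The first concerns which pregnancies are reported. The late-knowledge sentence has a lower limit at randomisation as well as an upper limit at Day 14. The lower limit removes a pregnancy that already existed when the study drug was taken, if nobody knew of it by Day 14. That pregnancy may have been exposed to both doses, and a pregnancy-reporting rule ought to catch it first.

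The second concerns what happens after a report. The protocol says that a serious outcome for mother or child is an SAE, but it has no step that finds out the outcome once Day 90 has passed.

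What is at stake is completeness of safety data for a small number of exposed pregnancies. Sample size, power and the primary analysis are not involved.

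**Working it through.** The protocol gives no figure to reproduce here. The check is day arithmetic with Day 0 as randomisation. Section 8.6 places the first dose as soon as possible after randomisation and the second about 24 hours after the first.

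**Inputs from the protocol**
- Pregnancy test: up to 7 days before treatment starts (6.2, 7.3).
- Reporting window: Day 0 to Day 14 (9.6).
- Late-known pregnancies: reported only if conception fell in Day 0 to Day 14 (9.6).
- Safety reporting ends at the Day 90 follow-up (9.3), with a visit window of ±7 days (Table 3).

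**Assumptions not in the protocol**
- A pregnancy test may stay negative for L days after conception, with L = 0, 7 or 14.
- Conception is 14 days after the last menstrual period (LMP).
- Term birth is at 37 to 42 weeks from LMP.

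**Step 1. Conceptions compatible with a valid negative test.** The earliest undetected conception is Day −(7 + L).
- L = 0: Day −7 to Day 0
- L = 7: Day −14 to Day 0
- L = 14: Day −21 to Day 0

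Even a perfect test leaves the week before treatment uncovered.

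**Step 2. Apply the 9.6 rule.**

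| Conception | Known by Day 14 | First known after Day 14 |
|---|---|---|
| Before Day 0, negative test | Report | Report not required |
| Day 0 to Day 14 (e.g. Day 13) | Report | Report |

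The one cell without a required report holds pregnancies that may have been exposed to both doses. A Day 13 conception, about 12 days after the second dose, is covered however late it is discovered.

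**Step 3. When the outcome is known.** For conception on day c, birth at w weeks from LMP falls on Day c − 14 + 7w.
- Earliest: c = −21, w = 37: −21 − 14 + 259 = Day 224
- Latest: c = 14, w = 42: 14 − 14 + 294 = Day 294
- Distance from Day 90: 224 − 90 = 134 days to 294 − 90 = 204 days

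Gestation at Day 90 is (90 − c + 14)/7 weeks: 12.9 weeks for c = 14 and 17.9 weeks for c = −21. If the call is made at Day 97, these become 13.9 and 18.9 weeks. No term birth from a conception near dosing can fall inside the reporting period.

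**Step 4. Does another section close the gap?** Section 9.4.2 follows ongoing SAEs, SARs and SUSARs to their final outcome. An uncomplicated pregnancy is none of these, because 9.6 does not treat pregnancy as an AE until a negative outcome is recorded. Table 3 and section 7.9 list an adverse event review at Day 14 and Day 90 but no pregnancy question. Discovery therefore rests mainly on the participant volunteering it under 6.1.

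**The case against.** The best reply is that the protocol is more protective than this suggests. Pregnant people and those planning to conceive are excluded, a negative test and contraception are required, and few pregnancies are to be expected. A pregnancy known by Day 14 is reportable whenever conception occurred. The opening sentence of 9.6 can be read as covering every pregnancy a participant reports. All of this stands except the last item: on that reading the two limiting sentences that follow would have no function, and a site cannot tell which reading applies.

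Three stronger conclusions that a reader might draw are not supported.

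- *That pregnancy-outcome SAEs can never be captured.* A pregnancy loss or a foetal anomaly known by Day 90 is an AE under 9.6, an SAE if serious, and falls within the period in 9.3. If still ongoing, it is followed under 9.4.2. The gap concerns later outcomes only.
- *That pregnant participants receive no follow-up.* Section 9.6 excludes only additional follow-up. The same paragraph keeps them in planned follow-up, including the adverse event reviews at Day 14 and Day 90.
- *That the participant's duty through Day 90 contradicts a site rule ending at Day 14.* A participant's duty to inform may be wider than what sites enter on an eCRF. Leaving out conceptions well after two doses may be deliberate, and Day 14 is also the cut-off for dexamethasone complications (3.3.1) and for individual onward reporting of SAEs to the sponsor (9.4). The number of days between Day 14 and Day 90 does not measure the gap, which concerns conceptions before Day 0.

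Nor does the protocol propose to draw conclusions about safety in pregnancy, so the point should not be presented as a threat to the trial's findings.

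**Conclusion.** Both gaps hold in limited form. First, a conception shortly before randomisation, compatible with a valid negative test and first known after Day 14, falls outside the reporting rule despite possible exposure to both doses. The vulnerable interval is at least Day −7 to Day 0, which follows from the protocol alone. It extends to Day −14 or Day −21 only if the test is assumed blind for 7 or 14 days after conception. Second, no procedure collects pregnancy outcomes arising after Day 90, while term births would fall at about Day 224 to 294 under the assumed gestation lengths.

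Severity: should-fix. The number of cases is probably a handful at most, and the primary analysis is not affected. The repair is nonetheless cheap, and the rule as written omits the more exposed pregnancy while covering the less exposed one.

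**What to change.** Amend section 9.6 in two places.

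(a) Reword the late-knowledge sentence to say, for example: *A pregnancy already present when study drug was taken, or conceived up to Day 14, is reported whenever it becomes known.* This also spares sites from having to place conception before or after randomisation.

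(b) Have the outcome of each pregnancy so reported recorded, for example by one records check or one call, with the participant's consent. State that a serious outcome, including congenital anomaly, is reportable as an SAE even after Day 90, and adjust the sentence on additional follow-up to match.

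Extending eCRF reporting to every conception up to Day 90 is not needed, and neither is any change to the contraception rules in 6.1 and 8.10. At most, the sponsor could be asked to reconcile 6.1, 8.10 and 9.6 by saying what a site does with a notified pregnancy that falls outside the reporting rule.

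Cost: an amendment to one section, one line in the consent form, and a check for probably a handful of participants. The downside is that those few cases stay open after Day 90.
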